4.3.1 SAEs exempt from reporting

Some events are anticipated as a result of the injury that has led to immobilisation of the spine, rather than the immobilisation itself. Many will be hospitalised with some requiring a stay in ICU/HDU. The following events will not need to be reported to WCTU because they are recorded in the CRF as an outcome or are anticipated as a result of the spinal injury rather than the intervention being studied:

- wound/skin breakdown
- pneumonia/chest infection
- evidence of intercranial hypertension
- other events directly attributable as a result of the participant's spinal injury

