1. BACKGROUND

1.1 Existing knowledge

NHS Ambulances use cervical collars for spinal immobilisation in large numbers of “at risk” injured patients (~ 80,000/year in UK, 5 million/ year in USA¹) but the numbers of patients shown to have a significant cervical vertebrae or spinal cord injury (SCI) is much less; 5476 in 2017 (from national major trauma registry, Trauma Audit & Research Network- TARN) with just under one third having cervical SCI (n=1376). A large number of patients are immobilised due to the challenges, even using the NICE decision rule, to confidently rule out unstable cervical spine (c-spine) fractures. Most civilian trauma is “blunt” (falls and road traffic collisions), where precise injury assessment is not possible in unconscious patients and difficult in conscious patients, who may have whiplash muscle injury, and may initially appear similar to a patient with an unstable spinal fracture. This means that at least 75% of patients exposed to the discomfort and complications of spinal immobilisation have no potential benefit. In the majority of immobilised patients, injuries to the spine are ruled out by assessment or imaging in the emergency department (ED) which allows removal of immobilisation within hours; however, ruling out an unstable spinal fracture may take much longer in comatose patients with brain injuries. Previous reports suggested that after imaging, 2-4% of major trauma patients have a significant c-spine injury. A published study using TARN data from 1998-2009 shows 2.3% of major trauma patients had a significant c-spine fracture or dislocation and 0.8% had a cervical SCI diagnosed prior to hospital discharge². The expansion of TARN to all trauma-receiving hospitals and better access to imaging has seen the average age of major trauma patients increase considerably in the intervening decade (current TARN median age = 59 years). The most recent analysis in 2017 suggests the true prevalence of significant potentially unstable c-spine injury and SCI within major trauma patients is therefore more than double (6% & 1.8% respectively). In the older population, cord contusion without fracture (e.g. central cord syndrome) is also more common. Recruitment will occur across the UK ensuring areas with a high disease burden make a substantive contribution.

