2.3.2 Safety

- Adverse events: pressure sores, aspiration pneumonia, intracranial hypertension.

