3.2.2 In hospital

The following data will be collected in hospital. These data will include:

- Duration of immobilisation in hospital
- Analgesia given (in hospital)
- CT scan appearance
- Details of cervical spine injury
- Mortality
- Evidence of infection
- The length of ICU stay and level of stay
- The length of hospital stay (dates)
- Interventions used for c-spine injury in the hospital and up to discharge
- Discharge destination
- Adverse events (e.g. chest infections, pressure sores, raised ICP)
- Other injuries sustained (randomisation to discharge)
- Injury Severity Score

The following will be collected as close as possible to the point of admission and discharge

- FIM (total and sub-scales)
- ASIA neurological scale
- Variables that will assist in the health economics analysis (including EQ-5D-5L/EQ-5D-Y).

If participants are discharged from the emergency department before a member of the local research team has had the opportunity to collect this data, their FIM-motor score will be recorded as 7 (total independence).

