4.3 Reporting Serious Adverse Events to the coordinating centre

The assessment and reporting of SAEs and related SAEs will follow the relevant Warwick CTU SOPs. Once a serious adverse event has been identified, information should be sent to the WCTU team at [contact], the WCTU QA team at [contact] and the Sponsor's Office at [contact] within 24 hours of the site becoming aware of the event. Reportable events should be recorded on the trial SAE form. The participant should continue to be followed-up until resolution of the event or a final outcome has been reached. Following reporting of a serious adverse event, any change of condition or other follow-up information should be reported by the same mechanism.

Events should be reported as a serious adverse event only if they:

- occur between randomisation and hospital discharge
- are serious (meet the criteria for Serious Adverse Events) AND are potentially related to trial participation, i.e. may have resulted from trial treatment;
- are not on the list of SAEs exempt from reporting (see section 4.3.1)

Examples of events that may be SAEs are;

- Use of one of the interventions causing a new injury that endangers the patient
- Unexpected cardiac arrest
- Sepsis related to use of collar
- Neuro-deficit

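### The unconditional SAE exemption in 4.3.1 removes the possibly treatment-related serious skin, chest and intracranial-pressure events from individual safety review

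*Protocol*

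**What the plan says.** Section 4.3 makes an event reportable as an SAE only if it meets three conditions together: it falls between randomisation and hospital discharge, it is serious and potentially related to trial participation, and it is not on the exempt list in 4.3.1.

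Section 4.3.1 opens with a statement about cause: "Some events are anticipated as a result of the injury that has led to immobilisation of the spine, rather than the immobilisation itself". It then gives two grounds joined by the word or. The first is "The following events will not need to be reported to WCTU because they are recorded in the CRF as an outcome". The second is that they are "anticipated as a result of the spinal injury rather than the intervention being studied". Four items follow: "wound/skin breakdown", pneumonia or chest infection, evidence of raised intracranial pressure, and a residual item for other events attributable to the spinal injury. No item is qualified by severity, by fatal outcome or by relatedness.

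The safety outcomes in 2.3.2 are "Adverse events: pressure sores, aspiration pneumonia, intracranial hypertension". Section 2.2.2 includes the same three among the outcomes used to assess the effect of the two techniques. The in-hospital data list in 3.2.2 has "Adverse events (e.g. chest infections, pressure sores, raised ICP".

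**The concern.** An exemption list normally spares sites from sending expedited reports of events that are frequent, expected and unrelated. In this protocol 4.3 has already screened out unrelated events before the list is reached, so the list can only act on events that someone thinks the technique may have caused. To justify that by saying the events come from the injury and not from the intervention contradicts the condition that brought them to the list.

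The trial compares two ways of restraining and positioning patients, and it chose skin, chest and intracranial-pressure events as its safety outcomes. A serious event of one of these kinds, suspected of being caused by the allocated technique, is a case that calls for individual review. As written, even a fatal one would have no route to it.

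**Working it through.** The plan states no figure on this point, so the check is a reading of the sections against one another.

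**1. What the exemption removes.** Reportable under 4.3 = in the time window AND serious AND potentially related AND not exempt. Take a serious pneumonia before discharge:
- If it is judged unrelated, it fails the relatedness condition and is not reportable, with or without 4.3.1.
- If it is judged potentially related, it meets every condition except the last, and 4.3.1 alone stops the report.

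For the three named event types, the set removed by the exemption is therefore the serious, potentially related set. Section 4.3.1 speaks of not reporting to the trials unit, but 4.3 makes the list a condition of SAE reporting as a whole, so the Sponsor's copy lapses too.

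**2. What those events then miss.**
- The 24-hour report (4.3).
- Causality assessment, which 4.4 requires for reportable SAEs.
- Expectedness assessment, which 4.4.2 applies to related SAEs following the investigator's causality assessment. Section 4.1 defines unexpectedness partly by severity, so an exempt event of unusual severity never meets that test.
- Notification of the ethics committee within 15 days if related and unexpected (4.4.3).
- The SAE report by randomised arm that goes to the DMC (4.4.3).

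A death is recorded on the CRF as an outcome (4.6), but that section provides no review of whether the technique contributed.

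**3. Whether other sections agree.** Section 4.4.1 says an event with a potential causal relationship should be reported to the trials unit. Section 4.5 makes the principal investigator responsible for reporting all SAEs to the Sponsor within 24 hours. Neither carries an exception for the list in 4.3.1. A site could follow either instruction.

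**4. Whether the first ground, outcome capture, covers the list.**

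| Exempt in 4.3.1 | Safety outcome in 2.3.2 | Example in 3.2.2 |
|---|---|---|
| any wound or skin breakdown | pressure sores | pressure sores |
| any pneumonia or chest infection | aspiration pneumonia | chest infections |
| intracranial hypertension | intracranial hypertension | raised ICP |

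The third row matches. In the first two the exempt term is wider than the named outcome, so some exempt events are not outcomes under 2.3.2.

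**5. Whether the second ground, spinal injury, suits the population.** Section 1.1 says that in most immobilised patients injury to the spine is ruled out in the emergency department. The trial enrols before imaging, on suspicion. For a participant without a spinal injury this ground has nothing to refer to. For one who has such an injury, it settles in advance a question that 2.2.2 sets out to examine.

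**The case against.** The strongest reply is that the two grounds are alternatives. For pressure sores, aspiration pneumonia and intracranial hypertension, capture as an outcome is enough by itself, whether or not the participant has a spinal injury. Recording expected events as outcomes instead of SAEs is a recognised choice, and 4.2 explains it by both techniques being in routine use. That stands: a reader might infer that both grounds fail, or that exempting the trial's own safety outcomes is a contradiction, and neither is so. Only the fourth list item itself names spinal injury, and the opening sentence refers more widely to the injury that led to immobilisation. Section 2.2.2 uses these events to assess the techniques; it does not assert that the techniques cause them.

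It also stands that oversight is not blind. Under 4.5 the DMC periodically reviews unblinded overall safety data, and under 7.10 it receives safety data and interim outcome assessments.

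Three further inferences go beyond the documents:
- That aspiration pneumonia cannot be derived. The list in 3.2.2 is given as examples and the CRF is not shown, so derivation is unconfirmed, not impossible.
- That the background statement, "at least 75% of patients exposed to the discomfort and complications of spinal immobilisation have no potential benefit", measures the problem. It describes a share of patients and their potential benefit, not a share of exempt events, and the outcome-capture ground does not depend on injury status.
- That listing "Sepsis related to use of collar" as a possible SAE contradicts the skin exemption. Sepsis is a separate event and stays reportable; that skin breakdown would be its source is not stated.

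The reply does not meet steps 1 to 3 of the working. Aggregate review by arm is a different safeguard from prompt assessment of one suspected case.

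**Conclusion.** The point holds in a limited form. For three event types, 4.3.1 removes from individual review the serious events that may have resulted from a technique, with no exception for death or threat to life, and it does not agree with 4.4.1 and 4.5. The terms exempted are wider than the outcomes that justify exempting them, and the spinal-injury rationale is a poor one for this population.

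The size is qualitative. Three of the four exempt items are affected. The number of events cannot be estimated, because the protocol gives no rates for them by severity, relatedness or injury status. No outcome data are lost, and sample size, error rates and the primary analysis are untouched. The conclusion assumes that the conditions in 4.3 apply together, as its wording indicates, and that no separate safety document overrides 4.3.1. It is worth correcting because it changes which events are reviewed individually, at little cost.

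**What to change.** - In 4.3.1, rest the exemption of the three named event types on outcome capture alone, and remove the attribution to spinal injury for them.
- Align the exempt terms with the outcomes in 2.3.2, so that nothing is exempt on the outcome ground unless it is recorded as an outcome.
- Keep fatal or life-threatening events of these types reportable under 4.3 when their relation to either technique is judged possible, probable or definite. Provide for that causality judgement to be made, since 4.4 now requires it only for reportable SAEs.
- Reconcile 4.4.1 and 4.5 with the revised list, so that sites have one instruction.
- Confirm that the CRF identifies aspiration among chest infections, and pressure-related or device-related cases among skin breakdown, so that the outcomes in 2.3.2 can be derived.

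The cost is a rewording of a few paragraphs, a check of the CRF (with an item added only if one is missing) and a small number of extra SAE reports. Few are expected, because 4.3 already limits reporting to potentially related events.

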4.4 Assessment of SAEs

For all reportable SAEs an assessment of the relationship between the SAE and the intervention should be done as per section 4.4.1 Assessment of causality.

4.4.1 Assessment of causality

Related SAEs are SAEs which are thought to have a potential for a causal relationship with the intervention. Causality should be assessed by a medical or clinical delegate of the PI at the investigator site. If an event is deemed to have a potential causal relationship, then this should be reported to WCTU via the mechanisms outlined in section 4.3. This should be followed by an expectedness assessment by an appropriately trained delegate of the Sponsor as per section 4.4.2 below.

The causality of SAEs (i.e. relationship to trial treatment) will be assessed by the investigator(s) on the SAE form using the following descriptions:

Relationship to trial medication	Description
Unrelated	There is no evidence of any causal relationship
Unlikely to be related	There is little evidence to suggest there is a causal relationship (e.g. the event did not occur within a reasonable time after administration of the trial intervention or device). There is another reasonable explanation for the event (e.g. the patient's clinical condition, other concomitant treatment).
Possible relationship	There is some evidence to suggest a causal relationship (e.g. because the event occurs within a reasonable time after administration of the trial intervention or device). However, the influence of other factors may have contributed to the event (e.g. the patient's clinical condition, other concomitant treatments).
Probable relationship	There is evidence to suggest a causal relationship and the influence of other factors is unlikely.
Definitely related	There is clear evidence to suggest a causal relationship and other possible contributing factors can be ruled out.

4.4.2 Assessment of expectedness

All related SAEs (Definitely, Probable or Possible) should be assessed against the known SAEs related to the intervention.

Expectedness assessment is the responsibility of the Sponsor and will be delegated to the coordinating centre in response to the causality assessments made by the investigator.

4.4.3 Expedited reporting of events to REC

The trial manager will liaise with the investigator to compile all the necessary information. The trial coordinating centre is responsible for reporting any related and unexpected SAEs to the sponsor and REC within required timelines. All other recruiting sites in the trial will be informed of the event and any implications for the trial.

All SAE reports will be reviewed on receipt by the Chief Investigator or Co-Chief Investigator (or their delegate). SAEs that are deemed to be unexpected and related to the intervention will be notified to the REC and sponsor within 15 days of receipt in accordance with regulatory requirements. All such events will be reported to the Sponsor, Trial Steering Committee and Data Monitoring Committee at their next meetings. Reports of all SAEs by randomisation arm will also be reviewed by the DMC at their regular meetings, or more frequently if requested by the DMC Chair.

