4.5 Responsibilities

Principal Investigator (PI):

Checking for AEs when participants are reviewed or followed-up.

1. Using medical judgement in assigning seriousness and causality

2. Ensuring that all SAEs are recorded and reported to the Sponsor within 24 hours of becoming aware of the event and provide further follow-up information as soon as available. Ensuring that SAEs are chased with Sponsor if a record of receipt is not received within 2 working days of initial reporting.
3. Ensuring that AEs are recorded and reported to the Sponsor in line with the requirements of the protocol.

Chief Investigator (CI) / delegate or independent clinical reviewer:

1. Clinical oversight of the safety of patients participating in the trial, including an ongoing review of the risk / benefit.
2. Immediate review of all SAEs
3. Review of specific SAEs in accordance with the trial risk assessment and protocol as detailed in the Trial Monitoring Plan.
4. Production and submission of annual reports to the relevant REC.

Sponsor or delegate (WCTU):

1. Central data collection and verification of AEs, and SAEs, according to the trial protocol.
2. Expectedness assessment of related SAEs
3. Reporting safety information to the CI, delegate or independent clinical reviewer for the ongoing assessment of the risk / benefit according to the Trial Monitoring Plan.
4. Reporting safety information to the independent oversight committees identified for the trial (Data Monitoring Committee (DMC) and / or Trial Steering Committee (TSC)) according to the Trial Monitoring Plan.
5. Expedited reporting of related and unexpected SAEs to the REC within required timelines.
6. Notifying Investigators of related and unexpected SAEs that occur within the trial.

Trial Steering Committee (TSC):

In accordance with the Terms of Reference for the TSC, periodically reviewing safety data and liaising with the DMC regarding safety issues.

Data Monitoring Committee (DMC):

In accordance with the Terms of Reference for the DMC, periodically reviewing unblinded overall safety data to determine patterns and trends of events, or to identify safety issues, which would not be apparent on an individual case basis.

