7.9 Trial Steering Committee (TSC)

The trial will be guided by a group of respected and experienced personnel and trialists as well as at least one PPI representative. The TSC will have an independent Chairperson. Face to face meetings

will be held at regular intervals determined by need but not less than once a year. Routine business is conducted by email, post or teleconferencing.

The Steering Committee, in the development of this protocol and throughout the trial will take responsibility for:

- Major decisions such as a need to change the protocol for any reason
- Monitoring and supervising the progress of the trial
- Reviewing relevant information from other sources
- Considering recommendations from the DMC
- Informing and advising on all aspects of the trial

The full remit and responsibilities of the TSC will be documented in the Committee Charter which will be signed by all members.

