7.10 Data Monitoring Committee (DMC)

The DMC will consist of independent experts with relevant clinical research, and statistical experience. The DMC will meet after the first 624 patients have been recruited and regularly every 6 months thereafter. Confidential reports containing recruitment, protocol compliance, safety data and interim assessments of outcomes will be reviewed by the DMC. The DMC will advise the TSC as to whether there is evidence or reason why the trial should be amended or terminated. In the unlikely event that the DMC recommends an early termination of the trial, whether due to safety concerns or for other reasons, a recommendation will be made immediately.

DMC meetings will also be attended by the Chief Investigator and Trial Manager (for non-confidential parts of the meeting) and the trial statistician.

The full remit and responsibilities of the DMC will be documented in the Committee Charter which will be signed by all members.

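### Related and unexpected SAEs go to the REC within 15 days but to the DMC only at its next meeting, with no alert to the DMC Chair in between

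*Protocol*

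**What the plan says.** Protocol section 4.4.3 sets two speeds for SAEs judged both related and unexpected. They "will be notified to the REC and sponsor within 15 days of receipt". For the oversight committees the rule is different: "All such events will be reported to the Sponsor, Trial Steering Committee and Data Monitoring Committee at their next meetings". The same section provides for by-arm reports of all SAEs at regular DMC meetings, "or more frequently if requested by the DMC Chair".

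Section 7.10 fixes the meeting cycle: "The DMC will meet after the first 624 patients have been recruited and regularly every 6 months thereafter". Section 7.9 says that face-to-face TSC meetings "will be held at regular intervals determined by need but not less than once a year", and adds: "Routine business is conducted by email, post or teleconferencing".

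Section 4.5 splits the sponsor's duties in the same way. Expedited reporting names only the REC. A separate duty, "Reporting safety information to the independent oversight committees identified for the trial", has no time limit and points to the Trial Monitoring Plan. Section 4.5 also gives the DMC the task of reviewing unblinded safety data for trends that would not show in individual cases.

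**The concern.** The DMC is the body charged with comparing harms between arms, yet the protocol's explicit rule makes it wait for a meeting while the REC hears within 15 days. Nothing in the protocol tells the DMC Chair that an event has happened, so nothing prompts the Chair to bring a review forward.

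These events are a narrow and informative set. Section 4.3 makes an SAE reportable only if it is potentially related to trial treatment and not on the exempt list. Those also judged unexpected are fewer still. The examples in section 4.3 include a new injury caused by an intervention and a neurological deficit. Several such events in one arm could accumulate between meetings before the DMC had compared the arms. Participants are enrolled before consent (sections 1.4 and 2.7), which gives independent by-arm oversight extra weight.

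**Working it through.** **Inputs**
- REC and sponsor limit: 15 days from receipt (4.4.3).
- DMC cycle: first meeting after 624 recruited, then every 6 months (7.10).
- Pilot target: 624 in 6 months, with thresholds at 75% and 30% (2.12).
- Planned total: 8,316 (6.1).
- Planned period: November 2022 to September 2025, with the pilot to 30 April 2023 and follow-up of 180 days (Trial Summary).

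**The plan's own figure.** The protocol gives no figure for notification delay. Its total sample size reproduces closely. With margin 2, SD 25.93, one-sided 0.025 and 90% power, n = 2 × (1.96 + 1.2816)² × 25.93² / 2², or 3,533 per arm. Then 3,533 / 0.85 = 4,157 per arm, or 8,314 in total, against 8,316 stated. I use 8,316 below.

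**Delay once the 6-monthly cycle is running**
- Longest wait: 365.25 / 2 = 182.6 days, about 183.
- Beyond the REC limit: 182.6 − 15 = 167.6 days, about 168.
- Mean wait if events fall evenly over the interval: 182.6 / 2, about 91 days.

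**Delay before the first DMC meeting.** That meeting is triggered by recruitment, so 6 months is not an upper bound. At a constant rate and with no sites added, the time to 624 patients is 6 months divided by the fraction of the pilot target achieved:
- 100%: 6 / 1 = 6 months
- 75%: 6 / 0.75 = 8 months
- 30%: 6 / 0.30 = 20 months

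**Participants randomised in one 6-month interval**
- Planned period 35 months, less 6 for the pilot and 6 for final follow-up: 23 months.
- Remaining participants: 8,316 − 624 = 7,692.
- Rate: 7,692 / 23 = 334 per month.
- In 6 months: 7,692 / 23 × 6 = 2,007, and 2,007 / 8,316 = 24%, or about 1,000 per arm.

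The 23 months is an assumption. With 18 recruiting months the 6-month figure is 7,692 / 18 × 6 = 2,564 (31%). With 29 months, leaving no time for final follow-up, it is 7,692 / 29 × 6 = 1,591 (19%).

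**Routes to the DMC between meetings.** Section 4.4.3 gives none for an individual event except the Chair's own request. Section 4.5 refers to the Trial Monitoring Plan without a time limit. Section 7.10 requires the DMC to pass on a termination recommendation at once, but it speeds only what leaves the DMC, not what reaches it.

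**The case against.** The strongest reply is that other safeguards act quickly, and this stands. Sites report within 24 hours (4.3). The CI or a delegate reviews every SAE on receipt (4.4.3, 4.5). Other recruiting sites are informed (4.4.3). The CI and sponsor can take urgent safety measures without a committee (4.7). The REC, itself independent, is told within 15 days and can mandate a stop (2.13). A reader might infer that nobody able to pause the trial learns in time; the documents do not support that.

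Three further inferences also go too far:
- **That the DMC Chair's right to more frequent reports is empty.** Section 4.4.3 does not make the request depend on knowing of an event, and the Chair could set a standing interval. What is missing is a trigger tied to an event.
- **That the TSC waits 12 months, with about 4,000 participants (48%) randomised meanwhile.** The yearly figure is a floor for face-to-face meetings. Section 7.9 also has the TSC meet by need and work by email and teleconference.
- **That the CI cannot see a cluster.** The trial is open-label (2.10.2) and no text blinds those who review SAEs. Equally, no text gives the CI by-arm totals.

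It is also fair to say that the Trial Monitoring Plan or the DMC charter, neither shown, may set a faster route. If so, that route needs reconciling with the explicit rule in 4.4.3.

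Finally, the 2,007 counts everyone randomised, not those at risk of cord injury. Section 1.1 gives about 80,000 immobilised a year, with 5,476 significant cervical injuries (6.8%) and 1,376 cervical cord injuries (1.7%). If the trial population is similar, which is an assumption, 2,007 would include roughly 137 and 35, across both arms. The protocol gives no SAE rate, so the number of events that could accumulate cannot be estimated.

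**Conclusion.** The point holds as a gap in event-driven notification of the DMC, not as an absence of any timely safeguard. Under the stated rule, the DMC may learn of a related and unexpected SAE up to about 183 days after receipt, or about 168 days after the REC limit. Before its first meeting the wait has no calendar limit. About 2,000 participants (24%) could be randomised in one interval, provided that the pilot reaches 624, recruitment uses all 23 remaining months and the planned dates hold. Slower recruitment would lower that number.

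Early review by the CI, sponsor and REC does not fully replace the DMC, because section 4.5 itself says the DMC's task is to find what single cases do not show. The change is cheap and bears on participant safety, so it is worth making.

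Section 4.4.3 also has a small inconsistency: it lists the sponsor both among those told within 15 days and among those told at their next meetings.

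**What to change.** In section 4.4.3:
1. Notify the DMC Chair of each related and unexpected SAE, with allocation, in parallel with the REC and within the same 15 days.
2. State that the Chair may then call an unscheduled by-arm safety review. Apply this from the first randomisation, so that it also covers the time before the first DMC meeting.
3. Inform the TSC Chair in parallel, without by-arm totals.
4. Keep cumulative tables for the regular meetings.
5. Remove the double listing of the sponsor.

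Align the Trial Monitoring Plan and DMC charter with this text. If either already sets such a route, cite it in 4.4.3 and change the sentence that now says otherwise.

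The cost is a short edit to 4.4.3 and the charter, one added notification to each Chair per event, and occasional extra review time for the DMC Chair.
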